	
marking all DP-selected suspicious PSLCs, the DP will verbally inform the Study Coordinator the Participant's Fitzpatrick skin phototype (1,2,3,4,5 or 6) after leaving the patient room.
 
Without dermatology Provider present, with Study Coordinator present:
 
The Participant will be asked to provide their Participant Mole Log Sheet (PMLS). Then, all PSLCs recorded in the PMLS will be entered into REDCap Cloud by the Study Coordinator. Any Participant-selected PSLCs that match those identified earlier as SUSPICIOUS by the DP will be marked with a horizontal line one (1) inch away from the target PSLC using a green surgical marker. Therefore, PSLCs identified by both the DP and Participant will have a plus symbol. Next, the Study Coordinator will take and record (near-perfect) SCI and DDI for all PSLCs recorded in the PMLS and those PSLCs identified by the DP as SUSPICIOUS (not matching the Participant PSLCs). Then, the Study Coordinator will complete the following:
 
 
1) Take one (1) photo of the Participant identification sticker with a Study Site secure smartphone/tablet
 
2) Take one (1) smartphone clinical image (SCI) of each target PSLC recorded in the Participant Mole Log Sheet (PMLS)
 
3) Take one (1) digital dermoscopy image (DDI) of each target PSLC using the Sklip dermatoscope.
 
4) Save the DDI of the target PSLC in the Study Site smartphone/tablet native photo gallery
 
5) Upload the Study Coordinator-taken DDI to the SMSA ("Scan Moles with Ai") within the Sklip App
 
6) Take one (1) screenshot the SMSA output
 
7) Record each SMSA output (SUSPICIOUS, UNREMARKABLE, ERROR) in REDCap Cloud, per target PSLC
 
8) If the Participant has taken a set of SCI/DDI at home of a PSLC that is not intended (qualified because of anatomic body site) for the Sklip System, the Study Coordinator should still capture a set of control SCI/DDI and upload to REDCap Cloud. The Participant standard clinical care will not be changed.
 
9) If the Participant took a set of SCI/DDI of a PSLC at home but did not follow instructions – specifically uploading the DDI to the Sklip System - the Study Coordinator should remind the Participant to complete this task in the patient room (using the DDI from their mobile device gallery), upload to the Sklip System, and record the output on their Mole Log Sheet. If this situation occurs, the Study Coordinator should make a note in REDCap Cloud; If the Participant is/was concerned about a PSLC but did not take a set of SCI/DDI at home, this PSLC will not be included in the study.
 

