## 2. OBJECTIVES AND ENDPOINTS

### 2.1 PRIMARY OBJECTIVES AND ENDPOINTS

Primary Objective	Endpoint	Start	End
Sklip System enables laypersons to safely triage self-selected pigmented skin lesions of concern from home with the same or better accuracy than pre-specified performance goals* for	Using all Participant PSLCs recorded in the Participant Mole Log Sheets, triage accuracy measures of the SMSA output of Participant-taken DDI will be assessed using a 2x2 table,	First day of enrollment	Up to 42 days after first day of enrollment

detection of pigmented skin lesions that require biopsy:
 
Melanoma and atypical melanocytic nevi with uncertain malignant potential (moderate, severe, and high grade atypia; those with pathology reports that include notes such as: borderline, cannot exclude melanoma, cannot exclude early evolving melanoma, unusual features, atypical spitz nevi, suspicion for melanoma, re-excision (or further removal) should be considered or is recommended in the pathologist management comment): ≥95% sensitivity, ≥30% specificity
 
Squamous cell carcinoma: ≥80% sensitivity, ≥30% specificity
 
Basal cell carcinoma: ≥80% sensitivity, ≥30% specificity
 
*Pre-specified performance goals have been reviewed with the FDA for testing the Sklip System (including SMSA) as a stand-alone device.
	
where the SMSA rating of “SUSPICIOUS” or “UNREMARKABLE” will be estimated to pre-specified accuracy metrics discussed with the FDA.
 
The Sensitivity of the SMSA using Participant-taken DDI will be estimated to pre-specified performance goals described in sections above, using 0.05 significance level and 10% margin of error.
 
Triage accuracy measures of the Sklip System (specificity, negative predictive value, positive predictive value, and accuracy) will also be calculated.
 
The Ground Truth will be the combination of the following described in the Sections above:
 
Dataset N) DDI dermoscopic diagnosis ground truth (DDI-GT) for PSLCs that were not biopsied during the In-Person Phase, and
 
Dataset O) Histologic diagnosis ground truth (H-GT) for lesions that were biopsied during the In-Person Phase
		
---	--	--	--

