### 3. STUDY DESIGN

#### 3.1 DESCRIPTION OF THE STUDY DESIGN

*Refer to Section 11, Statistical Analysis for additional information regarding statistical methods used in this Study.*

All Participants of this single-arm prospective trial will be given up to 14 days to **review** the Sklip System instructions, **perform** a self-skin-exam (SSE) at-home, and **identify** PSLCs based on the following:

- (a) General concern (self or partner-identified, or non-dermatology Provider identified requiring a referral to a dermatology Provider)
- (b) Concern because the PSLC is different than the rest (i.e. “ugly duck sign”)

Then, Participants will be instructed to carefully follow provided instructions and **complete** the following for each target PSLC:

- 1) Mark the target PSLC with a green surgical marker (horizontal line) and the number (#) corresponding to the mole log, one (1) inch away from the target lesion
- 2) Record the target PSLC with a number (#) and anatomic location in the PMLS
- 3) Create a new photo album titled: “Moles” in their native smartphone/tablet Photo App
- 4) Take one (1) smartphone clinical image (SCI) of the target PSLC, twelve (12) inches away from the target skin lesion
- 5) Save the SCI in the album titled: “Moles” album
- 6) Review Sklip dermatoscope instructions for proper use
- 7) Take one (1) digital dermatoscopy image (DDI) of the target PSLC using the Sklip dermatoscope.
- 8) Save the DDI of the target PSLC in the “Moles” album
- 9) Upload the DDI to the SMSA (“Scan Moles with Ai”) within the Sklip App once per target PSLC, until either a Suspicious or Unremarkable result is obtained, for a maximum of three attempts. If after three attempts the user still receives an “Error” result, they will be prompted to document this in the participant mole log sheet.
- 10) Take one (1) screenshot of the SMSA output per target PSLC
- 11) Save the SMSA output screenshot in the album titled: “Moles”
- 12) Record each SMSA output (SUSPICIOUS, UNREMARKABLE, ERROR) in the PMLS once per target PSLC
- 13) Contact the Study Site to schedule an in-person FBSE within 28 days, if the Participant does not already have a scheduled visit

In summary, for each target PSLC the Participant will acquire the following:

One (1) smartphone clinical image (SCI)  
One (1) digital dermoscopy image (DDI)  
One (1) Sklip Mole Scanning Algorithm (SMSA) output recorded in the PMLS  
One (1) SMSA output screenshot

---

End of At-home Phase-----

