## 6.1.7 PREPARATION

Once a Participant is officially enrolled in the Study, a designated Study Coordinator will properly sanitize and prepare a package of the necessary materials the Participant will need for the Study. The following are items that will be prepared to be shipped to the Participant via USPS or UPS:

- Instructions for Participants
- One (1) printed Participant Mole Log Sheet
- One (1) Sklip dermatoscope device (charging cable and dermoscopy oil)
- One (1) username/password enabling SMSA access using the Sklip App

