## 6.1.8 ADMINISTRATION

- 1) All necessary materials will be shipped to all Participants via USPS or UPS as described in 6.1.7 PREPARATION.
- 2) Study Coordinators will provide specific onboarding training:
  - a. The Participants will be trained on how to log their SSE self-selected PSLCs in their Participant Mole Log Sheet. They will also be asked to submit a copy of their Participant Mole Log Sheet using nPhase REDCap image upload, or email ([[contact]](mailto:[contact])). Participants will be reminded to bring it in person during their in-person visit.
  - b. The Participants will be informed on the requirement to follow up in-person for a FBSE with a Study Site dermatology Provider within 28 days of completing the At-home Phase.
  - c. The Participant will be informed that all costs associated with normal medical care activities will not be covered by the Study Sponsor as described in the sections above.

At the end of the Study, the Participants will be sent an nPhase REDCap Cloud survey that will document Participant responses to the number of self-selected PSLCs and the number of suspicious PSLCs identified by the dermatology Provider during the Study.

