### 8.1.8 ASSESSMENT OF STUDY AGENT ADHERENCE

Participants are not required to adhere to the interventional product. Frequency of use of the Study agent is measured and recorded (via Sklip analytics or nPhase REDCap Cloud survey), however use of the Study intervention is voluntary and at the discretion of the Participant.

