#### *Exploratory endpoint 4*

We will calculate the following based on Participant self-skin exams (SSEs) performed during the At-home Phase:

- (a) the mean and standard deviation of the number of PSLCs identified by Participants performing a SSE, and
- (b) the mean and standard deviation of the number of PSLCs identified by the dermatology Provider during the In-person Phase full body skin exam (FBSE).

The mean difference and 95% confidence interval will be calculated and assessed by paired t-test.

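### The participant's lesion list is not locked before the SMSA results are seen, so which lesions enter the primary table can depend on the test under study

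*Combined protocol and SAP*

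**What the plan says.** **Which lesions count.** Section 2.1 builds the primary 2x2 table "Using all Participant PSLCs recorded in the Participant Mole Log Sheets". Exploratory endpoint 4 uses "the mean and standard deviation of the number of PSLCs identified by Participants performing a SSE", which corresponds to Dataset A.

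**Order at home (3.1).** The participant does a self-exam and selects lesions by general concern or because one looks different from the rest. Each lesion is then marked on the skin (step 1) and logged: "Record the target PSLC with a number (#) and anatomic location in the PMLS" (step 2). Images follow, and step 9 is the upload "within the Sklip App once per target PSLC, until either a Suspicious or Unremarkable result is obtained", with at most three attempts. Step 12 writes the SMSA result on the same sheet.

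**Access.** The kit in 6.1.7 holds the blank sheet, the dermatoscope and "One (1) username/password enabling SMSA access using the Sklip App". The synopsis lets access run for up to 14 days from delivery, and the home phase is also up to 14 days.

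**Capture.** Section 6.1.8 says of participants: "They will also be asked to submit a copy of their Participant Mole Log Sheet using nPhase REDCap image upload", or by email, and has them reminded to bring the sheet to the visit. At the visit, once the provider has finished the exam, the synopsis and 3.1 have the coordinator key the study database from the sheet: "The Participant will be asked to provide their Participant Mole Log Sheet (PMLS). Then, all PSLCs recorded in the PMLS will be entered".

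**App records.** Sections 7.2 and 8.1.8 record frequency of app use. No section compares it with the log.

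**The concern.** In a diagnostic accuracy study, the set of lesions should be settled before the index test is read. Here an unsupervised participant holds the sheet and a working login together. A participant could scan a lesion first and then decide whether to log it, or could drop a logged lesion on a rewritten sheet. The UNREMARKABLE message in 6.1.1 advises self-monitoring, which gives a natural reason to stop regarding a lesion as one of concern.

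The omissions would fall on false negatives and true negatives. Suppose a lesion is scanned UNREMARKABLE, left off the sheet, and then found and biopsied by the blinded provider as melanoma. It would be handled as a provider-identified lesion absent from the log (Datasets I, J and K). It would not become a false negative in the primary table, although that is the error this safety-oriented endpoint most needs to count.

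Exploratory endpoint 4 has the same weakness. A list that can be revised after SMSA output does not cleanly measure lay self-examination.

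**Working it through.** **The plan's own figures**
- Formula (1) in 11.2 for melanoma sensitivity: 1.96² × 0.974 × 0.026 / (0.10² × 0.023) = 422.98, so 423 lesions.
- Participants: 423 / 1.5 × 1.10 = 310.2, stated as 310.
- Specificity projected in 11.2: Table 6 has 107 non-suspicious among 220 lesions negative for malignancy, and 107/220 = 48.6%, stated as 49%.

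All three reproduce. The point changes none of them.

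**Formulas.** Let w be the share of UNREMARKABLE lesions left off the log, taken as equal for malignant and benign lesions. The documents give no value for w.
- Observed Se = Se / [Se + (1 − Se)(1 − w)]
- Observed Sp = Sp(1 − w) / [Sp(1 − w) + (1 − Sp)]

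**Assumed true Se 90%, Sp 40%**

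| w | Observed Se | Observed Sp |
|---|---|---|
| 10% | 0.90/0.99 = 90.9% | 0.36/0.96 = 37.5% |
| 30% | 0.90/0.97 = 92.8% | 0.28/0.88 = 31.8% |
| 50% | 0.90/0.95 = 94.7% | 0.20/0.80 = 25.0% |

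No row meets both melanoma goals (95% and 30%). Observed Se reaches 95% only at w ≈ 53%, where Sp is about 24%.

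**Assumed true Se 92%, with the plan's projected Sp 49%, w = 40%**
- Se: 0.92 / (0.92 + 0.08 × 0.6) = 0.92/0.968 = 95.0%
- Sp: 0.49 × 0.6 / (0.294 + 0.51) = 0.294/0.804 = 36.6%

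Here a sensitivity below the goal reads as meeting it, and specificity still clears 30%.

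**If the SMSA performs at the plan's 97.4%.** w = 10% gives 97.7% (0.974/0.9974) and w = 50% gives 98.7% (0.974/0.987). The distortion is then small and changes no conclusion about sensitivity.

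**In lesions.** Table 6 expects 10 melanomas and 21 atypical nevi, so about 31 positives. Two misses give 29/31 = 93.5%. If one of the two is never logged, 29/30 = 96.7%. One lesion moves the point estimate across 95%.

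**Would the lesion count reveal it?** Table 6 has 257 suspicious and 166 non-suspicious lesions. At w = 50%, 257 + 83 = 340 remain, or 1.5 × 340/423 = 1.21 per participant. That lies inside the 1.02 to 1.9 images per participant cited in 11.2, so the count alone would not show the omission.

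**The case against.** Three safeguards are real. The instructed order puts selection, marking and logging before the scan, the SMSA result is not a selection criterion, and coordinators train participants on logging. The sheet is also not the only record: coordinators consult the images in the Moles album, and the end-of-study survey asks for the number of self-selected lesions. Provider-identified lesions missing from the sheet are imaged, and pathology is collected if they are biopsied. These are partial cross-checks. None locks the list before results are seen, and none has a stated role in deciding which lesions are analysed.

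The size is assumed. The documents give no w, and a lesion that worried the participant may well be logged whatever the scan says. The true sensitivities of 90% and 92% are not plan figures either.

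A reader might infer three stronger things that the documents do not support:
- **The list is first captured at the clinic.** Section 6.1.8 asks for a separate copy by upload or email, which may arrive earlier. The gap is that this copy has no due date and no governing role.
- **The plan permits scanning before logging.** The statement in 8.1.8 that "use of the Study intervention is voluntary and at the discretion of the Participant" concerns adherence and does not alter the order of steps in 3.1.
- **Selective logging will occur and carry a failing device to success.** The text leaves the route open but gives no evidence of its frequency. Several plausible inputs, including the plan's own 97.4%, produce no reversal.

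**Conclusion.** The point holds as a gap in control. The list that defines the primary lesion set, Dataset A and endpoint 4 is not locked before SMSA results are known, and nothing planned would measure whether logging depended on those results.

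If UNREMARKABLE lesions are left off, sensitivity is biased upward and specificity downward. The size cannot be derived from the documents. Across the illustrations it runs from 0.3 points of sensitivity (true 97.4%, w = 10%) to 4.7 points (true 90%, w = 50%). All figures are point estimates and rest on an assumed w that is equal in malignant and benign lesions. With about 31 expected positives in the melanoma and atypical nevus group, a single unlogged miss could matter.

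The change should be made because the guard is cheap and the endpoint is primary. This is not a finding that the planned analysis is invalid.

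**What to change.** 1. **Lock the list.** In 6.1.8 and step 2 of 3.1, require a photo of the lesion list (number and anatomic site only) through the existing REDCap image upload, after the self-exam and before the first SMSA scan. If the app allows it, activate the login on receipt. The documents do not show that this is possible, so treat it as optional. If it is used, the 14-day access period, which now runs from delivery, needs rewording.
2. **Name the governing version.** State that this time-stamped list is the source for Dataset A, exploratory endpoint 4 and the primary lesion set. Flag lesions added later and report them separately.
3. **Reconcile before database lock.** Compare app use per username and the Moles album with logged lesions and recorded attempts. Allow for up to three attempts per lesion and for clinic uploads under item 9 of 3.1.
4. **Add one sensitivity analysis.** Repeat the primary analysis without participants who have unexplained extra scans.

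The cost is one more participant step, with a possible short delay at the start of the home phase, plus coordinator time for the reconciliation. The sample size does not change. If the analytics hold only frequency of use, the app side of the reconciliation is limited to scan counts and cannot identify individual lesions.

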## LIST OF ABBREVIATIONS

CFR	United States Code of Federal Regulations
CoC	National Institutes of Health (NIH) Certificate of Confidentiality
CTCAE	Common Terminology Criteria for Adverse Events
DSMB	Data and Safety Monitoring Board
DSMC	Data and Safety Monitoring Committee
DSMP	Data and Safety Monitoring Plan
Ecris	Electronic Clinical Research Information System
HIPPA	Health Insurance Portability and Accountability Act
ICF	Informed Consent Form
IRB	Institutional Review Board
N/A	Not applicable
OHSU	Oregon Health & Science University
[SKLIP	
SYSTEM]	[Sklip dermatoscope device and SMSA (used in the Sklip App)]
SMSA	Sklip Mole Scanning Algorithm
SCI	Smartphone clinical images (non-medical-device assisted)
DDI	Digital dermatoscopy images
PSLC(s)	Pigmented skin lesion(s) of concern
FDA	United States Food and Drug Administration
PMLS	Participant Mole Log Sheet
SaMD	Software as a Medical Device
API	Application Program Interface
DP	Dermatology Provider
APP	Advanced Practice Practitioner (Physicians Associate or Nurse Practitioner)
PCP	Primary Care Provider
MD3PC	Modified dermatoscopy three-point checklist
DRFs	Dermoscopic remarkable features (based on the MD3PC)
SSE(s)	Self-skin-exam(s) performed by Participants at-home
FBSE(s)	Full body skin exam(s) performed by DPs in-office
SCI-TD	Expert dermatologist consensus SCI triage decision
DDI-GT	Expert dermatologist consensus DDI dermoscopic diagnosis
DHI	Digital histologic image of a target PSLC biopsied during the In-person Phase
EMR	Electronic medical record

## 1. BACKGROUND INFORMATION AND SCIENTIFIC RATIONALE

### 1.1 BACKGROUND

Reduced access: Appointment delays for skin lesion (mole) spot checks and FBSEs average 3-6 months nationally and were markedly increased during the COVID-19 Pandemic. Lack of access to a dermatology Provider (DP) is a result of limited number of DPs compared to the increasing population, low output of new DPs from MD/DO residency programs and NP/PA training programs compared to the rising population, understaffed clinics, and rising incidence of skin cancers that overwhelm the American healthcare system.

Shift to virtual care: There has been a monumental shift towards patient acceptance of virtual dermatology care in the last 36 months due to the Pandemic. Traditionally, virtual spot checks are performed using store-and-forward (SAF) patient-submitted SCI (non-medical-device assisted) that is evaluated by a DP. Accuracy of triage using SCI is lower than use of DDI for the same target skin lesion due to dermoscopy inherently providing more visual information through magnification and visualization of surface and subsurface structures that are not detectable when using the naked-eye in-office or SCI virtually.

Subjective selection bias of skin lesions (moles) of concern by patients at-home: Patients select PSLCs based on subjective concern and lack of professional triage training. A large portion of virtual visits initiated by patients result in reassurance by a DP that the PSLC is actually benign.

High conversion rate of virtual visits to in-person visits due to image clarity/selection bias: Evaluation of skin lesion images virtually using SCI typically results in low triage confidence by the DP. Provider uncertainty is largely due to limitations in image clarity and lack of medical-device assistance in an at-home environment. This often leads to a high conversion rate to an in-person evaluation by a DP. In the majority of cases the in-office DP, using a dermatoscope, will find that the PSLC is benign. This leads to patients being billed twice for triage for the same PSLC (1st = virtual visit, 2nd = in-person visit).

Packing the healthcare system can lead to delay of care for other patients: Layperson concern of unknowingly benign skin lesions can lead to overloading the healthcare system with unnecessary visits and increased delays for patients who may have an actual skin lesion that warrants biopsy, may be malignant, and ultimately requires equitable priority.

Interventional device: The Sklip System has been granted FDA Breakthrough Designation in 2021 (reported overall sensitivity of 94.47%) for its interpretation of DDI. The Sklip System will be made available to Study Participants via a non-commercial version of Sklip App with SMSA access via dedicated username and password (for research use only). The intended use of the Sklip System is stand-alone triage of PSLCs for skin cancer. Sklip System is intended for triage only (FDA Class 2). The Sklip System is not intended for diagnostic use (FDA Class 3). The reported Performance of SMSA for sensitivity of melanoma and atypical melanocytic nevi with uncertain malignant potential is 97.4%.

Study protocol intervention: We will test SMSA output from Participant-taken DDI of Participant-selected PSLCs in an at-home environment and evaluate real world performance of the Sklip System.

Potential intervention outcomes: The Sklip System may safely reduce submission of technically unclear images to DPs through its two-step SMSA algorithm. Use of the Sklip System requires a medical-device-assisted image (DDI) where the first step of the SMSA is to identify if the image is a DDI, then if the DDI is clear, in-focus and free of artifacts. If the DDI passes the first step, the SMSA then evaluates the uploaded DDI for presence of modified dermoscopy three-point checklist criteria. **The average time to obtain a Sklip System result is 5 seconds.** If positive, the lesion is flagged as SUSPICIOUS and information signals the Sklip System user to contact a healthcare Provider with urgency through clear product labelling in the Sklip Mole Analysis Report.

Hence, the Sklip System could potentially identify a malignancy with high sensitivity, safety and help prioritize layperson-to-patient triage pathway. Furthermore, for the purpose of access equity, the current publicly available commercial version of the Sklip App (since 03-2023) has a free-access map of every dermatology office location

in the United States. The Sklip app provides free contact information (phone and website) for the layperson to request to schedule a visit. Using the Sklip Network filter in the Sklip App map, verified dermatology offices willing to accept new patients for spot checks from the Sklip app within fourteen (14) days and without a referral from a primary care Provider are highlighted to the App user.

Possible intervention impact on the healthcare system: U.S. based academic centers represent only a small fraction of access to dermatologic care for the American public and access to high quality skin cancer screening using medical grade tools (including dermoscopy) is limited. Outside of academic settings there is a greater than fifty (50) percent chance that a layperson (new patient) will be seen in a dermatology office by an advanced practice practitioner (APP) (nurse practitioner or physicians associate). APPs working in a dermatology setting typically have a short two (2) week to (1) month rotation in dermatology during their schooling, prior to obtaining licensure to practice. APPs neither receive focused general dermatology training (3 year dermatology residency) nor dermoscopy training (3 years in dermatology residency), yet are expected to provide independent, high quality dermatologic care to patients, specifically during mole spot checks and full body skin exams. Many times they do not even use a dermatoscope, which is considered a standard of care for all graduates of a formal ACGME dermatologic residency program. Due to this limitation in training and experience, sensitivity of triage and diagnosis of skin cancers is often lower than a MD/DO dermatologist and often lower than a MD/DO primary care provider (overall reported dermoscopy sensitivity of 79.2% when using a dermatoscope).

The Sklip System can potentially empower both Providers and consumers that already have a concern about a pigmented skin lesion and do not have formal dermoscopy training, or multi-year experience, therefore offering the potential for safe improvement of triage accuracy in both office-based and home-based settings.

